4.7.2. Patient Global Impression of Severity (PGIS)

4.7.2.1. Patient Global Impression of Severity (PGIS)- Plantar Fibromatosis Overall

The participant will assess the overall severity of plantar fibromatosis using a 5-point scale ranging from 0 (“None”) to 4 (“Severe”) as per the SoA ([Table 2](#)).

4.7.2.2. Patient Global Impression of Severity (PGIS) – Foot Pain Subscale

The participant will assess the severity of foot pain using a 5-point scale ranging from 0 (“None”) to 4 (“Severe”) as per the SoA ([Table 2](#)).

4.7.2.3. Patient Global Impression of Severity (PGIS) – Difficulty Subscale

The participant will assess the overall difficulty for foot/feet for doing physical activities using a 5-point scale ranging from 0 (“None”) to 4 (“Severe”) as per the SoA ([Table 2](#)).

4.7.2.4. Patient Global Impression of Severity (PGIS) – Activity Limitation Subscale

The participant will assess the change in overall limitations in daily activities using a 5-point scale ranging from 0 (“None”) to 4 (“Severe”) as per the SoA ([Table 2](#)).

4.7.3. Patient Global Impression of Change (PGIC)

4.7.3.1. Patient Global Impression of Change (PGIC)- PF Overall

The participant will assess the overall severity of plantar fibromatosis using a 7-point scale ranging from –3 (“Very Much Worse”) to +3 (“Very Much Improvement”) as per the SoA ([Table 2](#)).

A responder is defined as a participant with a response of “Minimal Improvement”, “Much Improvement” or “Very Much Improvement” in the PGIC-PF Overall. All participants who withdrew early from the study will be considered as non-responders.

4.7.3.2. Patient Global Impression of Change (PGIC) – Foot Pain Subscale

The participant will assess the overall severity of foot pain using a 7-point scale ranging from –3 (“Very Much Worse”) to +3 (“Very Much Improvement”) as per the SoA ([Table 2](#)).

A responder is defined as a participant with a response of “Minimal Improvement”, “Much Improvement” or “Very Much Improvement” on the PGIC Foot Pain Subscale. All participants who withdraw early from the study will be considered as non-responders.

4.7.3.3. Patient Global Impression of Change (PGIC) – Difficulty Subscale

The participant will assess the overall difficulty for foot/feet for doing physical activities using a 7-point scale ranging from –3 (“Very Much Worse”) to +3 (“Very Much Improvement”) as per the SoA (Table 2).

A responder is defined as a participant with a response of “Minimal Improvement”, “Much Improvement” or “Very Much Improvement” on the PGIC Difficulty Subscale. All participants who withdraw early from the study will be considered as non-responders.

4.7.3.4. Patient Global Impression of Change (PGIC) – Activity Limitation Subscale

The participant will assess the change in overall limitations in daily activities using a 7-point scale ranging from –3 (“Very Much Worse”) to +3 (“Very Much Improvement”) as per the SoA (Table 2).

A responder is defined as a participant with a response of “Minimal Improvement”, “Much Improvement” or “Very Much Improvement” on the PGIC Activity Limitation. All participants who withdrew early from the study will be considered as non-responders.

4.7.4. Pain Intensity Numerical Rating Scale (NRS)

The participant will assess worst severity of overall foot pain ranging from 0 (“No Pain”) to 10 (“Worst Pain Imaginable”) as per the SoA (Table 2).

4.7.5. Subject Satisfaction with Treatment Scale (SSTS)

The participant will assess their satisfaction with treatment per treated foot using a 5-point scale ranging from -2 (“Very Dissatisfied”) to +2 (“Very Satisfied”) as per the SoA (Table 2).

The participant will assess the satisfaction with treatment separately for each treated foot, the assessment can be combined at participant level using worst case approach. If participant recorded a response as ‘Very Satisfied’ in one foot and ‘Quite Satisfied’ in another foot, then response will be considered as ‘Quite Satisfied’.

A responder is defined as a participant (by foot/feet) with a response of “Quite Satisfied” or “Very Satisfied” on the SSTS. All participants who withdraw early from the study will be considered as non-responders.

4.8. Investigator Assessments

4.8.1. Clinician Global Impression of Scale Change (CGIC)

The investigator will assess the degree of improvement per treated foot using a 7-point scale ranging from -3 (“Very Much Worse”) to +3 (“Very Much Improvement”) as per the SoA (Table 2).

As CGIC will be assessed for each treated foot. If participant is treated for both feet, then the assessment can be combined at participant level using worst case approach, if a response as ‘Minimal Improvement’ recorded in one foot and ‘Very Much Improvement’ in another foot, then response will be considered as ‘Minimal Improvement’.

A responder is defined as a participant (by foot/feet) with a response of “Minimal Improvement”, “Much Improvement” or “Very Much Improvement” on the CGIC. All participants who withdraw early from the study will be considered as non-responders.

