10. STATISTICAL CONSIDERATIONS AND METHODS

10.1. Sample Size Determination

The primary endpoint is the difference between EN3835 and placebo in the mean change from Baseline (Day 1) to Day 57 on the foot pain subscale (total score on 9 items) of the FFI ranging from 0 ("None") to 4 ("Extreme").

The sample size was estimated based on an interim analysis of the Day 57 data from Study EN3835-105, a dose-finding Phase 1 study. Assuming a difference in the mean change from Baseline to Day 57 in the pain subscale of FFI between EN3835 and placebo of 5.0 with a 10 standard deviation and 85% statistical power using a 2-sided test ($\alpha = 0.05$), 73 participants per treatment group (146 in total) will be needed to detect this difference between the 2 treatment groups. Assuming a dropout rate of 15%, the total sample size will be 172, eighty-six per treatment group for the study.

Participants will be screened to ensure that approximately 172 participants are randomized into 2 treatment groups, an EN3835 group and a placebo group in a 1:1 ratio.

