7.6. Efficacy Analyses

For the primary and key secondary efficacy endpoints, ITT Population will be the primary analysis population. Supportive efficacy analyses will also be performed using FAS and mITT Population. If the difference between FAS and mITT is no more than 5 participants, supportive analyses using FAS will not be generated. All the efficacy listing will be provided by ITT population.

For the data collected at nodule level, analyses will be performed at participant level and nodule level.

Table 27: List of Analyses Performed on All Efficacy Endpoints

Endpoint (Primary/ Secondary /Exploratory)	Endpoint	Primary analyses	Subgroup Analyses	Sensitivity Analyses	Supportive Analyses
Primary	The difference between EN3835 and placebo in the mean change from Baseline (Day 1) to Day 57 on the foot pain subscale (total score on 9 items) of the FFI ranging from 0 (“None”) to 4 (“Extreme”).	ANCOVA (ITT)	ANCOVA (ITT)	
 • MMRM based on (Observed Data) (ITT) • MMRM based on TPA (ITT) 	
 • ANCOVA (FAS) • ANCOVA (mITT)
1 st Key Secondary	The difference between EN3835 and placebo in the mean change from Baseline (Day 1) to Day 57 on the total score of the FFI pain and difficulty subscales (combined).	ANCOVA (ITT)	ANCOVA (ITT)	
 • MMRM based on (Observed Data) (ITT) • MMRM based on TPA (ITT) 	
 • ANCOVA (FAS) • ANCOVA (mITT)
2 nd Key Secondary	The difference in the proportion of EN3835-treated participants and those receiving only placebo reporting “Minimally Improved” (+1) “Much Improved” (+2) or “Very Much Improved” (+3) on the Clinician Global Impression of Change Scale, a 7-point scale ranging from –3 (“Very Much Worse”) to +3 (“Very Much Improvement”) at Day 57.	Cochran-Mantel-Haenszel method (ITT)	Cochran-Mantel-Haenszel method (ITT)	Cochran-Mantel-Haenszel based on TPA (ITT)	
 • Cochran-Mantel-Haenszel method (FAS) • Cochran-Mantel-Haenszel method (mITT)

Table 27: List of Analyses Performed on All Efficacy Endpoints (Continued)

Endpoint (Primary/ Secondary /Exploratory)	Endpoint	Primary analyses	Subgroup Analyses	Sensitivity Analyses	Supportive Analyses

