7.6.3.2. Key Secondary Endpoint 2: Clinician Global Impression of Change Scale

7.6.3.2.1. Key Secondary Endpoint 2: Primary Analyses

The 2nd key secondary estimand is defined by the following:

- **The *secondary* clinical question of interest is:** In participants with plantar fibromatosis, what is the difference in the proportion of EN3835-treated participants and those receiving only placebo reporting “Minimally Improved” (+1) “Much Improved” (+2) or “Very Much Improved” (+3) on CGIC, a 7-point scale ranging from –3 (“Very Much Worse”) to +3 (“Very Much Improvement”) at Day 57 between EN3835 and placebo, regardless of discontinuation of study intervention?
- **Treatment condition:** Randomized study intervention (EN3835 or placebo)
- **Target Population:** Adult participants with plantar fibromatosis who are included in the ITT Population.
- **Variable (Endpoint) of interest:** Difference in the proportion of participants reporting a response on the CGIC, a 7-point scale ranging from –3 (“Very Much Worse”) to +3 (“Very Much Improvement”) at Day 57
- **Treatments being compared:** The difference in proportion of participants reporting a response on the CGIC at Day 57 will be compared between EN3835 and placebo.
- **Intercurrent Event:** The treatment policy strategy will be adopted for the analyses.
 - Any new or change in concomitant treatment will not be adjusted for primary analyses.
 - Early withdrawal from the study is the potential intercurrent event that could occur. All participants who withdraw early from the study will be considered as non-responders. The responder is defined as a participant who reports a score to be “Minimal Improvement”, “Much Improvement” or “Very Much Improvement” on the CGIC at Day 57.
- **Population Level-Summary measure:** The stratum adjusted risk difference, associated 95% CI and p-value will be presented.
- **Method of Analyses:** The difference in proportion of responders between EN3835 and placebo will be analyzed using Cochran-Mantel-Haenszel (CMH) test stratified by total number of nodules at baseline. The stratum adjusted risk difference, associated 95% CI and p-value will be presented using CMH test. The frequency and percentage of responders and 95% CI will be provided based on the Wilson (Score) by treatment group.

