7.6.4.3.1. Patient Global Impression of Change - PF Overall Score

The difference in proportion of responders between EN3835 and placebo will be analyzed using CMH test stratified by baseline severity score (ie, PGIS-PF Overall) separately for each visit.

The stratum adjusted risk difference (RR) from the CMH test, associated 95% CI and p-value will be presented separately for each visit. The frequency and percentage of responders (Section 4.7.3.1) and 95% CI will be provided based on the Wilson (Score) by treatment group and visit.

The degree of improvement in the 7-point scale as determined by the investigator using PGIC – PF overall will be summarized using frequency and percentages with mean and SD by each treatment group and visit.

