7.6.4.8. Nodule Consistency – Responder Analyses

7.6.4.8.1. Participant Level Analyses: Change in consistency from Baseline to Day 15, 29, 43 and 57 in the Nodule Consistency

The difference in proportion of responders between EN3835 and placebo will be analyzed using CMH test stratified by baseline nodule consistency separately for each visit.

The stratum adjusted risk difference, associated 95% CI and p-value will be presented separately for each visit. The frequency and percentage of responders (Section 4.6.1) and 95% CI will be provided based on the Wilson (Score) by treatment group and visit (ie, Days 15, 29, 43, and 57).

The degree of improvement in nodular consistency will be summarized using frequency and percentages with mean and SD by each treatment group and visit (ie, Days 15, 29, 43, and 57).

A listing of nodule consistency will be provided by participant.

7.6.4.8.2. Nodule Level Analyses: Change in consistency from Baseline to Day 15, 29, 43 and 57 in the Nodule Consistency

The difference in proportion of responders between EN3835 and placebo will be analyzed using CMH test stratified by baseline nodule consistency separately for each visit and each nodule.

The stratum adjusted risk difference, associated 95% CI and p-value will be presented separately for each visit. The frequency and percentage of responders (Section 4.6.1) and 95% CI will be provided based on the Wilson (Score) by treatment group and visit (ie, Days 15, 29, 43, and 57).

The degree of improvement in nodular consistency will be summarized using frequency and percentages with mean and SD by each treatment group and visit (ie, Days 15, 29, 43, and 57) for each treated nodule.

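### Key secondary 2 (CGIC responders at Day 57) adjusts only for number of nodules and leaves out baseline PGIS-PF Overall, so some precision may be lost in a test that gates key secondary 3

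*SAP*

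**What the plan says.** **Scoring.** CGIC is rated per treated foot. SAP 4.8.1 states: "If participant is treated for both feet, then the assessment can be combined at participant level using worst case approach". Any of the three improvement grades counts as response, and early withdrawals count as non-responders.

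**Analysis.** In SAP 7.6.3.2.1 the difference in responders is "analyzed using Cochran-Mantel-Haenszel (CMH) test stratified by total number of nodules at baseline". No other factor is named. Protocol 10.3.1.2.2 specifies CMH and a stratum-adjusted risk difference without naming the stratum, so the choice of stratum is the SAP's.

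**Other responder scales.** PGIC overall uses a "CMH test stratified by baseline severity score (ie, PGIS-PF Overall) separately for each visit" (SAP 7.6.4.3.1). Each PGIC subscale uses its matching PGIS subscale (7.6.4.3.2 to 7.6.4.3.4). Satisfaction uses PGIS-PF Overall (7.6.4.5) and is also combined across feet by the worse foot (4.7.5). Nodule consistency uses a "CMH test stratified by baseline nodule consistency separately for each visit" (7.6.4.8).

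**Place in the hierarchy.** SAP 6.5 tests the primary endpoint, then key secondaries 1, 2 and 3, each at 0.05 and each only if the one before succeeds.

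**The concern.** CGIC is the only responder endpoint inside the error-controlled sequence, and the only responder scale whose comparison takes no account of baseline severity or consistency. PGIS is recorded at Screening and Day 1, and whether one or both feet were treated is also known. Randomisation names no stratification factor (Protocol 7.5, SAP 3.6), so chance imbalance in severity is left to the analysis. If baseline severity predicts the CGIC rating, leaving it out makes the treatment comparison less precise than it need be. A lost step at key secondary 2 also ends formal testing of key secondary 3. No reason is given for treating CGIC differently from satisfaction.

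**Working it through.** **1. The plan's own figure.** Protocol 10.1 assumes a difference "between EN3835 and placebo of 5.0 with a 10 standard deviation" and states "85% statistical power using a 2-sided test ($\alpha = 0.05$), 73 participants per treatment group (146 in total) will be needed". The normal approximation gives n = 2 × (1.960 + 1.036)² × (10/5)² = 71.8, so 72 per arm. The noncentral t gives 73 (power 0.851). For dropout, "Assuming a dropout rate of 15%, the total sample size will be 172, eighty-six per treatment group for the study": 146/0.85 = 171.8, so 172. The figure reproduces, but it concerns FFI pain. Neither document gives a response rate or power for key secondary 2. I carry forward only 86 per arm and 15% dropout; the remaining inputs are assumptions.

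**2. Does feet treated matter?** With foot-level response p and between-foot correlation ρ, a bilateral participant responds with probability p² + ρp(1−p). At ρ = 0.5:
- p = 0.40: 0.16 + 0.5 × 0.24 = 0.28
- p = 0.65: 0.4225 + 0.5 × 0.2275 = 0.536

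The worse-foot rule lowers response in both arms, while the arm difference barely moves (0.25 against 0.256). Take 25% bilateral (the background figure in Protocol 3.1, not a trial forecast). In the placebo arm, variance explained by feet treated is 0.25 × 0.75 × (0.40 − 0.28)² = 0.0027. The overall rate is 0.75 × 0.40 + 0.25 × 0.28 = 0.37, and 0.37 × 0.63 = 0.233, so the share is about 1.2%. Nodule count already carries part of this: under exclusion criteria 4 to 6 a count of 1 is always unilateral and 4 always bilateral, so only counts 2 and 3 mix the two.

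**3. Power by simulation, first set.** 86 per arm, 4,000 runs per row, Monte Carlo error about 0.7 points. Assumed: foot-level response 40% vs 60%, 25% bilateral, 15% dropout as non-response, three equal severity levels, nodule count not prognostic. Entries are power (%).

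| Severity log-odds per level | Other between-participant variation | CMH by nodules (plan) | CMH by nodules × feet | CMH, all three crossed | Main-effects adjusted | Adjusted minus plan |
|---|---|---|---|---|---|---|
| 0 | yes | 62.1 | 62.2 | 59.2 | 62.4 | +0.3 |
| 0.5 | yes | 62.1 | 61.9 | 58.2 | 62.6 | +0.5 |
| 1.0 | yes | 63.8 | 64.0 | 63.1 | 66.6 | +2.8 |
| 1.0 | none | 63.7 | 64.0 | 65.1 | 69.0 | +5.3 |
| 1.5 | none | 62.9 | 62.4 | 68.2 | 72.2 | +9.3 |

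The last two rows remove all other variation between participants, so they mark the optimistic end. Adding feet treated to the nodule strata moves power by at most 0.5 points here, and by 0.6 (66.4 to 67.0) with 50% bilateral. Crossing all three factors loses 2.9 and 3.9 points in the first two rows, because cells become sparse.

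**4. Second set.** 45% vs 70%, 86 per arm, 4,000 runs. Adjusted against planned power is 81.5% vs 81.4% when neither severity nor nodule count is prognostic (+0.1), and 85.5% vs 81.2% at a severity odds ratio of 2.5 per SD (+4.3). Adjustment lost power in no case run. Replacing nodule count by PGIS × feet strata lost about 1 to 3 points when nodule count was prognostic and severity was not.

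**5. Type I error.** With equal arms, rejection was 5 to 6% for the stratified tests and about 5% for the adjusted risk difference.

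**The case against.** The planned choice is coherent. Number of nodules is a covariate in the primary, key secondary 1 and key secondary 3 models, so stratifying key secondary 2 by it keeps the four tests aligned. The protocol names CMH. PGIC and satisfaction are participant-reported, whereas CGIC is an investigator's rating of change, made by investigators blinded to the participants' scales (Protocol 7.5), and it has no baseline value. That PGIS predicts it is an assumption.

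Most of this stands. It is why nodule count should be kept and why the gain is stated only as possible. The alignment argument cuts both ways, though: the other three models also include the outcome's own baseline value, and key secondary 2 has no severity term at all.

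A reader might infer from the worse-foot rule that feet treated is the important missing factor. The documents do not support that. Nodule count is a partial proxy under the eligibility limits, and adding feet treated changed power by less than 1 point in every scenario run. A reader might also infer that PGIS × feet should replace nodule count as the stratum. That swap can lose power, and the SAP defines no PGIS grouping coarser than its five levels.

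**Conclusion.** The point holds as a possible loss of precision. Key secondary 2 omits a baseline severity measure that is already collected and that the SAP uses for closely related endpoints. The planned test is valid, and type I error is not affected. It would go too far to say that precision is demonstrably lost: the documents give no CGIC response rates, between-foot correlation or prognostic strength.

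Under the assumptions shown, the gain from adjustment is about 0 to 4 points of power for severity odds ratios from 1 to 2.5 per SD. It was larger only where severity was made to explain all variation between participants. Nearly all of it comes from severity. This is an inexpensive improvement and does not threaten the trial's conclusions.

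**What to change.** Before unblinding, in SAP 7.6.3.2.1 and the matching row of Table 27:

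- Make the key secondary 2 analysis one pre-specified covariate-adjusted (standardised) risk difference with a robust standard error. Use main effects only: treatment, baseline PGIS-PF Overall, number of nodules, and feet treated (1 vs 2). State how each is coded.
- Report the nodule-stratified CMH as supportive.
- Record the departure from the protocol's CMH method in SAP Table 28.
- Do not drop nodule count in favour of PGIS × feet strata, and do not cross all three factors; either can lose power.

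The by-visit CGIC analysis in SAP 7.6.3.5.1 follows the key secondary 2 approach, so say whether it changes too. The CGIC tipping-point steps are blacked out in the public SAP, so I cannot say what they would need.

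Cost: SAP wording and programming, with no new data. The drawbacks are a change from the protocol-named method and a gain near zero if severity is only weakly prognostic.

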4.9. Safety Parameters

4.9.1. Adverse Events

AE verbatim terms as reported by the investigator will be mapped to System Organ Class (SOC) and Preferred Term (PT) using the Medical Dictionary for Regulatory Activities (MedDRA).

4.9.1.1. Treatment-Emergent Adverse Events

A TEAE is any condition that was not present prior to treatment with study intervention but appeared following treatment, was present at treatment initiation but worsened during treatment, or was present at treatment initiation but resolved and then reappeared while the individual was on treatment (regardless of the intensity of the AE when the treatment was initiated).

Refer to Section [6.3.4.1](#) to identify TEAE status when start date of an AE is unknown.

4.9.1.2. Intensity of Adverse Events

Intensity (or severity) of AEs will be graded as Grade 1 to 5 according to the CTCAE Version 5.0.

For AEs with missing grade, no imputation will be performed, and the AE will be analyzed with the missing grade. If the intensity of an AE changes, then the most severe intensity during the continuous episode will be recorded.

4.9.1.3. Relationship to Study Intervention

The causal relationship with study intervention will be classified by the investigator and will be reported as follows:

- Not related
- Unlikely related
- Possibly related
- Probably related

Related adverse events are TEAEs with the relationship described by the investigator as “probably related” or “possibly related”. “not related” or “unlikely related” causality assessments are considered as not related.

Any missing relationship of an AE to study intervention will be considered as related to study intervention for the analyses, following worst case principle.

4.9.2. Clinical Laboratories and Vital Signs

4.9.2.1. Potentially Clinically Important Laboratory Values

Sponsor determined potentially clinically important (PCI) laboratory values are presented in [Table 22](#).

Table 22: Potentially Clinically Important Laboratory Criteria

Parameter	PCI Low: ≤Or =	PCI High: ≥ Than Or =
Hemoglobin (g/L)	100	190
Hematocrit (%)	30	60
Platelets (10 ⁹ /L)	100	650
ALT (U/L)		3×ULN
AST (U/L)		3×ULN
Creatinine (μmol/L)		200
BUN (mmol/L)		14

ALT=alanine transaminase; AST=aspartate transaminase; BUN=blood urea nitrogen; ULN=upper limit of normal

4.9.2.2. Potentially Clinically Important Vital Sign Values

Vital sign values are PCI, if they meet both the observed value criteria and the change from Baseline. The sponsor determined PCI criteria are presented in Table 23.

Table 23: Potentially Clinically Important Vital Sign Criteria

Parameter	PCI Low	PCI High
Systolic blood pressure	≤90 mmHg and decrease ≥20 mmHg from baseline	≥140 mmHg and increase ≥20 mmHg from baseline
Diastolic blood pressure	≤60 mmHg and decrease ≥15 mmHg from baseline	≥100 mmHg and increase ≥15 mmHg from baseline
Pulse rate	≤50 bpm and decrease ≥15 bpm from baseline	≥125 bpm and increase ≥15 bpm from baseline
Respiratory rate	≤12 brpm and decrease ≥7 brpm from baseline	≥25 brpm and increase ≥7 brpm from baseline
Temperature		≥38.3° C and increase ≥1.1 °C from baseline

PCI=potentially clinically important; bpm=beats per minute; brpm=breaths per minute.

